3.2 Trial Treatments

Brexipiprazole will be administered orally as one tablet once a day for 14 weeks. Although the temporal relationship between IMP administration and meals will not be considered, subjects should take the IMP at the specified time in so far as possible. The IMP doses are shown in Table 3.2-1. IMP administration will be initiated at 0.5 mg and the dose will be increased to 1 mg after evaluation at Week 1 (Day 8) and to 2 mg after evaluation at Week 2 (Day 15). If the investigator or subinvestigator judges that dose increase to 2 mg is difficult for safety reasons based on the subject's condition after evaluation at Week 2 (Day 15), the dose may be maintained at 1 mg (see [Section 3.2 1](#) Dose Maintenance at 1 mg). From Week 2 (Day 15), the dose may be reduced or increased to 1 or 2 mg if the investigator or subinvestigator decides that dose adjustment is necessary (see [Section 3.2 2](#) Dose Change). In cases where dose reduction to lower than 1 mg is required, the trial should be discontinued.

Table 3.2-1 Doses of IMP		
Day 1-7	Day 8-14	Day 15-98
0.5 mg	1 mg	1 mg or 2 mg

1) Dose Maintenance at 1 mg

If the investigator or subinvestigator decides that dose increase to 2 mg is difficult due to the occurrence of an adverse event (AE) identified from the evaluation at Week 2 (Day 15), the dose will be maintained at 1 mg. The AE for which this judgement was made will be recorded in the case report form (CRF).

2) Dose Change

If the investigator or subinvestigator decides that dose adjustment is necessary based on the subject's condition, the dose will be reduced or increased to 1 or 2 mg.

If the investigator or subinvestigator decides that the current dose is not sufficiently effective, the dose will be increased to 2 mg. If either of the following cases applies, the dose will be reduced to 1 mg and the reason for dose reduction will be recorded in the CRF. In the event that both of the following cases apply, the AE should be recorded as the reason for dose reduction. When the occurrence of an AE necessitates dose reduction, enter "dose reduction" in the CRF as the action taken for the AE in relation to IMP administration.

The dose may be reduced to 1 mg in the following cases:

- Dose reduction is necessary because an AE has occurred.
- Dose reduction is necessary because symptoms have improved.

3.3 Trial Population

A total of 157 male and female patients with agitation associated with dementia of the Alzheimer's type who have completed the treatment period of Trial 331-102-00088 and whose condition can be observed by a caregiver in at least 4 days per week for 4 hours or more a day.

3.4 Trial Visit Window

For all endpoints, acceptable windows for analysis are specified, and analysis should take place at the analysis time points regardless of time points recorded on the case report form.

Acceptable windows for analysis are shown in Table 3.4-1. Day 1 is defined as the day when treatment with the IMP begins. If multiple data exist within an acceptable window, the last data within the window will be used in analysis. Data obtained 7 days or later after the final dosing will be excluded from the analysis.

Table 3.4-1	Acceptable Windows for Analysis	
Week	Target Day	Trial Day Interval
Baseline	1	- 1
Week 1	8	2 - 11
Week 2	15	12 - 22
Week 4	29	23 - 36
Week 6	43	37 - 50
Week 8	57	51 - 64
Week 10	71	65 - 78
Week 12	85	79 - 92
Week 14	99	93 - 113

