Week 10	Day 71	Day 68 to Day 74
Week 12	Day 85	Day 82 to Day 88
Week 14	Day 99	Day 96 to Day 106
Follow-up period	28 days after the final administration of IMP	23 to 35 days after the final administration of IMP

The date of starting IMP administration is designated as Day 1, and the day before initiation of IMP treatment is designated as Day -1.

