3.8.4.1 Alzheimer's Disease Cooperative Study—Activities of Daily Living (ADCS-ADL)

The rater will review the answers to the 19 questions on the dementia patient's activities of daily living through an interview with the caregiver using the ADCS-ADL severe dementia version and will record the results. The evaluation will be made on the basis of information for the period from 28 days before each evaluation date. If the caregiver cannot come to the trial site for a compelling reason, an interview by telephone is acceptable for the follow-up observation only.

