6.7 Analysis of Other Endpoints

Analysis of other endpoints will be performed using the safety analysis set. Baseline is defined as the last data obtained prior to initiation of IMP treatment in this trial.

- ADCS-ADL
- MMSE

For ADCS-ADL total score and MMSE total score, descriptive statistics of actual measurements and changes from baseline at each time point and the final assessment (Week 14 LOCF) will be calculated.

7 Management of Investigational Medicinal Product

Refer to the investigator's brochure on brexpiprazole and the separately-specified manual for details regarding IMP management.

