CT-11.3 Listing of Potentially Clinically Relevant Abnormalities in Vital Signs (Safety Analysis Set)
CT-11.4 Summary of Mean Change From Baseline by Study Week in Body Weight (kg) (Safety Analysis Set)
CT-11.5 Summary of Mean Change From Baseline by Study Week in BMI (kg/m²) (Safety Analysis Set)
CT-11.6 Incidence of Potentially Clinically Relevant Weight Gain or Loss by Baseline BMI (Safety Analysis Set)
CT-12.1 Mean Change From Baseline in ECG Results (Safety Analysis Set)
CT-12.2 Shift Tables of ECG (Safety Analysis Set)
CT-12.3 Incidence of Categorical Increases in QT Evaluations (Safety Analysis Set)
CT-12.4 Incidence of Potentially Clinically Relevant Abnormalities in ECG Evaluations (Safety Analysis Set)
CT-12.5 Listing of Potentially Clinically Relevant Abnormalities in ECG Evaluations (Safety Analysis Set)
CT-13.1 Summary of Mean Change From Baseline by Study Week in DIEPSS (Safety Analysis Set)
CT-13.2 Summary of Mean Change From Baseline by Study Week in AIMS Total Score and Item Scores 8, 9 and 10 (Safety Analysis Set)
CT-13.3 Summary of Mean Change From Baseline by Study Week in BARS, Global Clinical Assessment of Akathisia (Safety Analysis Set)
CT-14.1 Summary of Mean Change From Baseline by Study Week in Sheehan-STS Score (Safety Analysis Set)
CT-14.2 Summary of Mean Change From Baseline by Study Week in Sheehan-STS - Total Score (Safety Analysis Set)
CT-14.3 Summary of Mean Change From Baseline by Study Week in Sheehan-STS - Suicidal Ideation Subscale Score (Safety Analysis Set)
CT-14.4 Summary of Mean Change From Baseline by Study Week in Sheehan-STS - Suicidal Behavior Subscale Score (Safety Analysis Set)
CT-15.1 Summary of Mean Change From Baseline by Study Week in ADCS-ADL Total Score (Safety Analysis Set)
CT-15.2 Summary of Mean Change From Baseline by Study Week in MMSE Total Score (Safety Analysis Set)

Appendix 5

List of Subject Data Listings

AE-1	Adverse Events (Subjects Assigned to Treatment)
DEMOG-1	Demographic Characteristics (Subjects Assigned to Treatment)
DREAS-1	Discontinued Subjects and Reason for Discontinuation (Subjects Assigned to Treatment)
LAB-1	Laboratory Test Results: Serum Chemistry (Subjects Assigned to Treatment)
LAB-2	Laboratory Test Results: Hematology (Subjects Assigned to Treatment)
LAB-3	Laboratory Test Results: Urinalysis (Subjects Assigned to Treatment)
LAB-4	Laboratory Test Results: Other Laboratory Tests (Subjects Assigned to Treatment)
LAB-5	Pregnancy Test (Subjects Assigned to Treatment)

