EFF-1	Cohen-Mansfield Agitation Inventory (CMAI) (Subjects Assigned to Treatment)
EFF-2	Clinical Global Impression - Severity of Illness (CGI-S) (Subjects Assigned to Treatment)
EFF-3	Clinical Global Impression - Improvement (CGI-I) (Subjects Assigned to Treatment)
PDATA-1.1	Inclusion and Exclusion Criteria (Subjects Assigned to Treatment)
PDATA-1.2	Inclusion and Exclusion Criteria (Screening Failures)
PDATA-2	Treatment Assignment List (Subjects Assigned to Treatment)
PDATA-3	Study Completion Status and Reasons for Discontinuation (Subjects Assigned to Treatment)
PDATA-4	Medical History (Subjects Assigned to Treatment)
PDATA-5	Alzheimer's Disease History (Subjects Assigned to Treatment)
PDATA-6	Patient Care (Subjects Assigned to Treatment)
PDATA-7.1	Prior and Concomitant Medications (Subjects Assigned to Treatment)
PDATA-7.2	Prior and Concomitant Therapy (Subjects Assigned to Treatment)
PDATA-8	Physical Examination (Subjects Assigned to Treatment)
PDATA-9	Vital Signs (Subjects Assigned to Treatment)
PDATA-10	Electrocardiogram Results (Subjects Assigned to Treatment)
PDATA-11.1	Sheehan-Suicidality Tracking Scale (S-STS) - Other than Q15 and Q16 (Subjects Assigned to Treatment)
PDATA-11.2	Sheehan-Suicidality Tracking Scale (S-STS) - Q15 (Subjects Assigned to Treatment)
PDATA-11.3	Sheehan-Suicidality Tracking Scale (S-STS) - Q16 (Subjects Assigned to Treatment)
PDATA-12	Drug-Induced Extrapyramidal Symptoms Scale (DIEPSS) (Subjects Assigned to Treatment)
PDATA-13	Barnes Akathisia Rating Scale (BARS) (Subjects Assigned to Treatment)
PDATA-14	Abnormal Involuntary Movement Scale (AIMS) (Subjects Assigned to Treatment)
PDATA-15	Mini-Mental State Examination (MMSE) (Subjects Assigned to Treatment)
PDATA-16	Alzheimer's Disease Cooperative Study - Activities of Daily Living (ADCS-ADL) (Subjects Assigned to Treatment)
PDATA-17	Post-treatment Follow-up (Subjects Assigned to Treatment)
PDATA-18	Screening Failures
PDEV-1	Major Protocol Deviations by Type of Deviation (Subjects Assigned to Treatment)
SMED-1	Study Medication Administration (Subjects Assigned to Treatment)
SMED-2	Study Medication Compliance (Subjects Assigned to Treatment)
SUBEX-1	Subjects Excluded From Analysis Set (Subjects Assigned to Treatment)

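### Does the SAP's 7-day post-dose cut-off wrongly leave the follow-up ADCS-ADL interview out of the summaries?

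*SAP*

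**What the plan says.** SAP section 3.4 assigns data on all endpoints to the analysis windows of Table 3.4-1 and adds: "Data obtained 7 days or later after the final dosing will be excluded from the analysis". The last window is Week 14 (Days 93 to 113). There is no follow-up row.

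On ADCS-ADL, Protocol section 3.8.4.1 bases the rating on "information for the period from 28 days before each evaluation date" and says that, if the caregiver cannot attend, "an interview by telephone is acceptable for the follow-up observation only". Protocol Table 3.8-2 sets the follow-up visit at "23 to 35 days after the final administration of IMP" and the Week 14 visit at "Day 96 to Day 106".

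On reporting, Protocol section 6.7 plans the following, along with a Week 14 LOCF value: "For ADCS-ADL total score and MMSE total score, descriptive statistics of actual measurements and changes from baseline at each time point". SAP section 13 says the same. The table planned for this in SAP Appendix 4 is CT-15.1, "Summary of Mean Change From Baseline by Study Week in ADCS-ADL Total Score (Safety Analysis Set"). SAP Appendix 5 lists ADCS-ADL by subject (PDATA-16) and has a separate listing, PDATA-17, "Post-treatment Follow-up (Subjects Assigned to Treatment").

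**The concern.** Read together, these sections seem to disagree. The protocol appears to collect a functional rating about four weeks after the drug is stopped and plans statistics at every time point. The SAP then excludes anything obtained a week or more after the last dose and gives follow-up no window. Caregivers would supply information on function after withdrawal, and no summary would show it.

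The same sentence raises two further questions:

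- The Week 14 visit may be as late as Day 106, while the dosing table ends at Day 98. A completer seen on time by the protocol's rule could lose the Week 14 value.
- Protocol section 3.6.1 lists adverse events among the safety endpoints. A rule introduced for all endpoints could be read as discarding events that arise after treatment, in a trial whose main purpose is safety.

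**Working it through.** Let L be the day of the last dose. An observation on Day d is excluded when d − L ≥ 7.

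**Follow-up ADCS-ADL.** Inputs: follow-up on L+23 to L+35 (Protocol Table 3.8-2); 28-day rating period (Protocol 3.8.4.1).

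- Permitted days: 35 − 23 + 1 = 13. The earliest is 23 days after the last dose, and 23 ≥ 7, so all 13 are excluded whatever L is.
- Off-drug share, taking the rating period as the 28 days ending the day before the interview: min(28, d − 1) days for an interview d days after the last dose. At d = 23 this is 22 of 28; at d = 28 it is 27 of 28; from d = 29 it is 28 of 28.

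A follow-up rating is therefore almost wholly an off-drug measurement. It could not be pooled with Week 14 or carried into LOCF.

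**What the cut-off protects.** Follow-up visits of subjects who stop early could otherwise land in the Week 14 window. That needs L + 35 ≥ 93 and L + 23 ≤ 113, so L from 58 to 90. Without the cut-off, their off-drug values could be counted as Week 14 results.

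**Week 14.** Inputs: visit window Days 96 to 106 (11 days); last dosing day 98 in the SAP dose table. Days lost = max(0, 106 − (L + 7) + 1).

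| Last dose | Excluded visit days | Number of 11 |
|---|---|---|
| Day 97 | 104 to 106 | 3 |
| Day 98 | 105, 106 | 2 |
| Day 99 | 106 | 1 |
| Day 100 or later | none | 0 |

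Protocol section 3.8.1.4 supplies drug up to the next assessment, and SAP section 9.1 has an exposure category above 98 days, so dosing up to a late visit is foreseen. Where the loss does occur, exclusion is defensible. CMAI rates the previous 14 days (Protocol 3.8.3.1). After a last dose on Day 98, a Day 105 visit covers Days 91 to 104, of which 99 to 104 (6 of 14) are off drug. A Day 106 visit covers Days 92 to 105, of which 99 to 105 (7 of 14) are off drug.

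**Adverse events.** No arithmetic applies. SAP section 3.4 concerns visit windows, and its tie-break keeps the last record in a window, which makes no sense for events. SAP section 9.2 gives adverse events their own onset intervals, the last of which is for events after trial treatment. Protocol section 5.2 collects events to the end-of-trial date. Taken together, the sections keep post-treatment events in the tables.

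**The case for a change.** The strongest case for a change starts from the telephone allowance, which has no purpose unless ADCS-ADL is rated at follow-up. It cannot refer to the preceding trial's follow-up, because rollover subjects skip that visit (Protocol 3.1). If the rating is made, leaving it out of the tables narrows a plan to describe every time point. SAP section 15 records comparably small departures, such as how QTc categories are summarized, yet its visible text does not mention this one. At Week 14 the loss could matter for LOCF. Diaries are issued at Weeks 2 and 12 for the CMAI assessments (Protocol 3.8.1.4), which implies ratings at Weeks 4 and 14. An excluded Week 14 CMAI would then be replaced by a value about 10 weeks older.

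Much of this stands as description. The follow-up rating is likely, the day counts are right, and the SAP does not say in words that it is only listed.

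Two steps do not stand. First, no broken commitment is shown. SAP section 3.4 defines its own analysis time points, CT-15.1 is by study week, and Protocol section 6.7 names no follow-up time point, so the time points in question are most naturally those of Table 3.4-1. Second, the absence of a summary cannot be asserted firmly. The follow-up columns of the schedule cannot be read in the available text, where the ADCS-ADL row shows one mark after baseline, as the MMSE row does. Part of SAP section 15 is redacted. The LOCF point needs both an early last dose and a visit in the last days of the window, and the observed Week 14 summary is reported beside LOCF.

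**Conclusion.** No change to the plan is needed. Followed as written, it gives sound on-treatment summaries, keeps off-drug ratings out of Week 14 and LOCF, and leaves any follow-up ADCS-ADL value in the subject listings. Listing an off-drug value of an endpoint in the protocol's other category, without tabulating it, is a fair choice for an uncontrolled trial of 14 weeks' treatment. SAP section 6 plans no primary or secondary outcome, so no test or safety conclusion moves.

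If ADCS-ADL is rated at follow-up, all 13 permitted days are outside the summaries for every subject interviewed. At Week 14 the loss is 2 of 11 visit days for a last dose on Day 98, 1 for Day 99 and none from Day 100. The number of subjects affected cannot be computed from the documents. Any completer affected can be identified from the score listings and the dosing listing (SMED-1). For adverse events, SAP section 9.2 already settles the matter.

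What remains is a small gap in wording: the SAP could say whether follow-up ADCS-ADL is only listed or shown as a separately labelled post-treatment time point. Analysts applying SAP section 3.4 would list it, which is sensible. This conclusion assumes that the follow-up interview takes place, as Protocol section 3.8.4.1 implies, and that the 28-day rating period ends the day before the interview.

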3.5 Handling of Endpoints

3.5.1 Cohen-Mansfield Agitation Inventory (CMAI)

The CMAI total score will be the sum of scores for 29 CMAI items.

The CMAI Aggressive Behavior score will be the sum of scores for CMAI Items 3, 4, 7, 8, 9, 10, 11, 13, 14, 15, 21, and 25.

The CMAI Physically Non-aggressive Behavior score will be the sum of scores for CMAI Items 1, 2, 16, 22, 26, and 29.

The CMAI Verbally Agitated Behavior score will be the sum of scores for CMAI Items 5, 6, 18, and 19.

3.5.2 Clinical Global Impression - Severity of Illness (CGI-S)

“0. Not assessed” will be handled as missing data.

3.5.3 Clinical Global Impression - Improvement (CGI-I)

“0. Not assessed” will be handled as missing data.

3.5.4

[REDACTED]

[REDACTED]

[REDACTED]

[REDACTED]

3.5.5

3.5.6 Drug Induced Extra-Pyramidal Symptoms Scale (DIEPSS)

The DIEPSS total score will be the sum of scores for DIEPSS items 1 through 8.

3.5.7 Abnormal Involuntary Movement Scale (AIMS)

The AIMS total score will be the sum of scores for AIMS items 1 through 7.

3.5.8 Sheehan Suicidality Tracking Scale (S-STS)

The S-STS total score will be the sum of scores for Item 1a, Items 2 through 11, highest of Item 12 or any row of Item 16, highest of Item 14 or any row of Item 15, Item 17, and Item 20.

The S-STS suicidal ideation subscale score will be the sum of scores for Items 2 through 11.

The S-STS suicidal behavior subscale score will be the sum of scores for Item 1a, highest of Item 12 or any row of Item 16, highest of Item 14 or any row of Item 15, Item 17, and Item 20.

3.5.9 Alzheimer's Disease Cooperative Study - Activities of Daily Living (ADCS-ADL)

The ADCS-ADL total score will be the sum of scores for ADCS-ADL Items 1 through 19.

3.5.10 Mini-Mental State Examination (MMSE)

The MMSE total score will be the sum of scores for MMSE Items 1 through 30.

4 Sample Size

This trial aims to include 100 completers of brexpiprazole treatment in Trial 331-102-00088 as subjects who will continue to receive brexpiprazole for more than 10 weeks. Since patients are assigned to the 1 mg group, the 2 mg group, or the placebo group at a ratio of 3:4:4 in Trial 331-102-00088, the target sample size for this trial (331-102-

00184) has been determined to be 157 subjects, taking into account some of them have received placebo in the previous trial.

5 Statistical Analysis Datasets

Analyses in this trial will be performed for each of the following groups unless otherwise specified:

- Rollover subjects from the brexpiprazole group in Trial 331-102-00088
- Rollover subjects from the placebo group in Trial 331-102-00088
- All subjects (rollover subjects from the brexpiprazole group + rollover subjects from the placebo group)

5.1 Efficacy Analysis Set

The efficacy analysis set will comprise subjects who have received at least 1 dose of the IMP and from whom CMAI total scores have been obtained at baseline and at least 1 time point after initiation of treatment.

5.2 Safety Analysis Set

The safety analysis set will comprise subjects who have received at least 1 dose of the IMP.

5.3 Handling of Missing Data

For analyses at the final assessment, the last observation carried forward (LOCF) method (in which missing Week 14 data are imputed by the data which were observed after initiation of IMP treatment and obtained immediately before Week 14) will also be used.

6 Primary and Secondary Outcome Variables

Neither primary nor secondary outcome variables are planned.

7 Disposition and Demographic Analysis

7.1 Subject Disposition

Numbers and proportions of subjects from whom informed consent was obtained, those who received trial treatment, those who completed the trial, those who discontinued the trial, those who discontinued the trial by reason for discontinuation, and those included in each analysis set will be summarized.

7.2 Demographic and Baseline Characteristics

Descriptive statistics (mean, standard deviation, minimum, median, and maximum; hereinafter the same applies) of age, height,^a baseline body weight, and baseline body mass index (BMI), and frequency distribution of age category (< 80, \geq 80) (< 65, \geq 65 to < 75, \geq 75), sex,^a race,^a ethnicity,^a country where trial is conducted,^a complications,^a medical history,^a and dose used in the previous trial will be determined in each analysis set.

^aData obtained at screening in Trial 331-102-00088 will be used.

7.3 Baseline Disease Evaluation

Descriptive statistics of the duration of dementia of the Alzheimer's type,^a duration of agitation associated with dementia of the Alzheimer's type,^a [REDACTED] [REDACTED] CGI-S, CMAI (total score, subscale scores), MMSE total score, and ADCS-ADL total score, and frequency distribution of medical care category,^b prior use of antipsychotics (yes or no),^a type of caregiver,^b and concomitant use of antidementia drugs (yes or no).

^aData obtained at screening in Trial 331-102-00088 will be used.

^bData obtained at the start of the present trial will be used.

The duration of dementia of the Alzheimer's type and the duration of agitation associated with dementia of the Alzheimer's type will be calculated using the following formula: duration (months) = (date of subject demographic evaluation – date of onset + 1) / 30. Any unknown month or day of onset will be replaced with June or 15, respectively.

7.4 Treatment Compliance

Treatment compliance (number of days when the subject actually received the IMP/number of days for which the IMP was prescribed) will be grouped into < 70%, \geq 70% to < 80%, \geq 80% to < 90%, and \geq 90%, and the frequency distribution will be determined in the efficacy analysis set.

7.5 Prior and Concomitant Medications

Numbers and proportions of subjects who used medications before, during, and after the treatment period will be determined by drug class and preferred term of the World Health Organization Drug Dictionary (WHODD) version Global B3 March 2018 in the safety analysis set.

7.6 Protocol Deviations

Numbers and proportions of subjects with major deviations from the protocol will be determined for each category (IMP administration, eligibility criteria, a failure to discontinue the trial when the subject meets the withdrawal criteria, procedures that affect evaluation of the primary endpoint, use of prohibited medications, and overall) at each trial site in the safety analysis set.

8 Efficacy Analysis

Efficacy analyses will be performed on the efficacy analysis set. Baseline is defined as the last data obtained prior to initiation of IMP treatment in this trial.

- CMAI total score
- CMAI subscales (Aggressive Behavior, Physically Non-aggressive Behavior, and Verbally Agitated Behavior)
- CGI-S
- CGI-I

For endpoints other than CGI-I, descriptive statistics of actual measurements and changes from baseline at each time point and the final assessment (Week 14 LOCF) will be calculated. For CGI-I, descriptive statistics of actual measurements at each time point and the final assessment (Week 14 LOCF) will be calculated.

